Progressive disease (PD)	Evidence for a n increase in bone marrow blast percentage and/or increase of a bsolute blast counts in the blood: >50% increase in marrow blasts over baseline (a minimum 15% point increase is required in cases with <30% blasts at baseline; or persistent marrow blast percentage of >70% over at least 3 months; without at least a 100% improvement in ANC to an a bsolute level (>0.5 x 10^9 /L [500/µL], and/or platelet count to >50 x 10^9 /L [50,000/µL] nontransfused); or >50% increase in peripheral blasts (WBC X% blasts) to >25 X 10^9 /L (>25,000/µL) (in the absence of differentiation syndrome); or New extramedullary disease
Relapse	
Hematologic relapse (a fter CR _{MRD} -, Cr, CR _i)	Bone marrow blasts ≥5%; or reappearance of blasts in the blood; or development of extra medullary disease
Molecular relapse (after CR _{MRD} -)	If studied pretreatment, reoccurrence of MRD as a ssessed by RT-qPCR or by MFC

^a The period of stable disease should be at least 3 months to be considered SD.

Confidential Page 44 of 74

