Potential patients for the study may be screened/enrolled:

- Prior to their first allogeneic HSCT. Leukapheresis material, from the HSCT donor, for the production of MT-401 will be obtained as a separate collection from the HSCT or ~30 days after, based on donor status at time of collection.

or

- When experiencing their first relapse post-allogeneic transplant. The same HSCT donor must be available and agree to undergo leukapheresis for production of MT-401.

Patients eligible for the study will be placed into one of two groups:

- **Adjuvant (Group 1):** Patients screened prior to their HSCT with CR without minimal residual disease (CR_{MRD}-) at 80 days post-transplant based on central testing will be randomized (1:1) in an unblinded fashion to:
 - MT-401 (Arm A)
 - SOC - observation (Arm B)

Randomization will be stratified by pre-transplant MRD status (MRD⁺ vs. MRD⁻/Unknown) and cytogenetic risk (Unfavorable vs. Other). However, randomization will be performed only if MRD testing performed centrally at Baseline visit (~80 days post-transplant) is negative.

Note: Patients whose product includes fewer cells or does not meet specifications may be treated with MT-401.

- **Active Disease: (Group 2):** Patients meeting the following criteria will be assigned to Subgroup C (frank relapse) or Subgroup D (MRD⁺) in Group 2 and will receive MT-401:
 - Patients in Group 1 who experience relapse (patients with MRD [MRD⁺] or frank relapse) prior to randomization
 - Patients in Arm B of Group 1 (SOC) who experience relapse (MRD⁺ or frank relapse) after randomization (crossover patients)
 - Patients who do not consent prior to HSCT but are experiencing their first relapse (MRD⁺ or frank relapse) and have the same donor available for manufacturing

Note: Patients in Group 2 may receive bridging chemotherapy for \leq 6 months prior to receiving MT-401. Additionally, patients that meet the eligibility criteria for Group 2 only can be used for the Safety Lead-in portion of the study.

Those patients who enter the study prior to HSCT must meet applicable inclusion/exclusion criteria prior to and following HSCT for study entry and must agree to provide bone marrow aspirate sample(s) to be held for testing.

Relapse is defined as bone marrow blasts \geq 5%, or reappearance of blasts in the blood, or development of extramedullary disease, or development of MRD positivity after having a post-treatment MRD negative status.

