Disease assessments will be performed by local and central laboratory facilities. Screening assessments for Group 1 patients can be a prior disease assessment completed within 45 days of screening as per SOC. For Group 1, pre-transplant testing of MRD should be performed locally

by any testing methodology and results recorded in eCRF. Post-transplant baseline MRD testing will be performed centrally and results must be available prior to randomization. MRD⁺ will be defined as CR (including normalization of counts) with detection in blood, bone marrow or any other tissues by flow cytometry and/or molecular testing (eg, PCR, next generation sequencing).

The study will evaluate safety and efficacy endpoints in post-HSCT patients after the infusion of MT-401 using standard methods of assessment (peripheral blood and bone marrow evaluation, positron-emission tomography [PET] scan, etc.). Response will be evaluated using the European LeukemiaNet (ELN) recommendations and repeated MRD assessment. Historical data will inform the clinical relevance of the magnitude and durability of response in Group 2 and will supplement data from the concurrently randomized control arm in Group 1 (Arm B). A synthetic control arm may also be identified for Group 2C. If created, the specifications of this control arm and analysis methods to be used will be documented in a separate statistical analysis plan.

The Data Monitoring Committee (DMC) will review data after the first 45 RFS events in Group 1 have been observed to assess safety and evaluate estimates of RFS for possible Group 1 enrollment expansion. Additionally, the sponsor will review safety and efficacy data in Group 2 after the first 10 patients per subgroup have progressed or had the opportunity to be followed for 6 months.

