For Group 1, randomization codes will be prepared to allow the clinical study sites to enroll patients by using an interactive response technology (IRT) system. Treatment group assignments will be known to site personnel (ie, investigator, pharmacist, and study staff) and patients. After completion of required screening procedures, patients will be assigned, using the randomization schedule, to MT-401 vs observation (SOC) with a 1:1 allocation. The randomization schedule will be created with stratification factors of pre-transplant MRD status (MRD⁺ vs. MRD⁻/Unknown) and cytogenetic risk (Unfavorable vs. Other) using random block sizes. SOC patients in Group 1-Arm B who relapse after randomization may cross over to Group 2 to receive MT-401, if the subgroup is open and/or Sponsor agreement.

For Group 2, after the patient's eligibility is established and informed consent has been obtained, the patient will be enrolled, and a number will be assigned through the IRT. Since this is a single-arm cohort, all enrolled patients who meet eligibility criteria will be treated with MT-401.

Due to the nature of the administration of MT-401 along with the fact that the endpoints are objectively evaluated without the concern for bias, the study is not blinded.

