Progressive disease (PD)	Evidence for an increase in bone marrow blast percentage and/or increase of absolute blast counts in the blood: 
 • >50% increase in marrow blasts over baseline (a minimum 15% point increase is required in cases with <30% blasts at baseline; or persistent marrow blast percentage of >70% over at least 3 months; without at least a 100% improvement in ANC to an absolute level ($>0.5 \times 10^9/L$ [$500/\mu L$]), and/or platelet count to $>50 \times 10^9/L$ [$50,000/\mu L$] nontransfused); or • >50% increase in peripheral blasts (WBC X % blasts) to $>25 \times 10^9/L$ ($>25,000/\mu L$) (in the absence of differentiation syndrome); or • New extramedullary disease
Relapse	
Hematologic Relapse (after CR _{MRD-} , CR, CR _i)	Bone marrow blasts $\geq 5\%$; or reappearance of blasts in the blood; or development of extramedullary disease
Molecular relapse (after CR _{MRD-})	If studied pretreatment, reoccurrence of MRD as assessed by RT-qPCR or by MFC

^a The period of stable disease should be at least 3 months to be considered SD.

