6.4.1.2 Primary Efficacy Variables

Phase 2 Adjuvant (Group 1):

- RFS: defined as the time between the date of randomization and the date of first relapse per ELN recommendations or death by any cause, whichever occurs first. Relapse includes either hematologic and/or molecular relapse as defined in [Table 2](#) at any disease assessment. In the event that no relapse or death is documented prior to analysis cutoff or the start of new anti-cancer therapy, RFS will be censored on the date of the last evaluable disease assessment demonstrating no relapse prior to analysis cutoff or the start of new therapy. For patients who remain alive and have no baseline disease assessment or have no post-randomization disease assessment, RFS will be censored on the date of randomization. In addition, if relapse or death occurs after extended time without disease assessments, RFS will be censored on the date of the last evaluable disease assessment prior to the missed disease assessments.

For patients with relapse or death, a variable will be created to flag whether the earlier date of relapse or death occurs after extended time without disease assessments. The extended time is defined as below:

- Time from randomization date to Day 0 visit + 12 weeks + assessment window of 2 weeks, if the latest assessment prior to the event (relapse or death, whichever is earlier) \leq randomization date + 0.5*time from randomization date to Day 0 visit. For patients without Day 0 visit, an artificial Day 0 visit will be derived as randomization date + mean time from randomization date to Day 0 visit date in MT-401 arm, for analysis purpose only.
- 24 weeks + assessment window of 2 weeks, if the latest assessment prior to the event (relapse or death, whichever is earlier) \leq Day 0 visit + 6 weeks & $>$ randomization date + 0.5*time from randomization date to Day 0 visit
- 38 weeks + assessment window of 5 weeks, if the latest assessment prior to the event (relapse or death, whichever is earlier) \leq Day 0 visit + 18 weeks & $>$ Day 0 visit + 6 weeks
- 78 weeks + assessment window of 5 weeks, if the latest assessment prior to the event (relapse or death, whichever is earlier) \leq Day 0 visit + 37 weeks & $>$ Day 0 visit + 18 weeks
- 104 weeks + assessment window of 5 weeks, if the latest assessment prior to the event (relapse or death, whichever is earlier) \leq Day 0 visit + 78 weeks & $>$ Day 0 visit + 37 weeks

Phase 2 Active Disease (Group 2):

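### RFS and Arm B crossover rest on different definitions of molecular relapse, so an MRD-positive SoC patient can cross over without an RFS event

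*SAP*

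**What the plan says.** **Endpoint.** SAP 6.4.1.2 defines RFS from randomization to first relapse or death. It says "Relapse includes either hematologic and/or molecular relapse as defined in" Table 2, and Protocol 9.3.2 refers in the same way to Table 6. The molecular-relapse row of SAP Table 2 reads "If studied pretreatment, reoccurrence of MRD as assessed by RT-qPCR or by MFC". The same row of Protocol Table 6 opens identically: "If studied pretreatment, reoccurrence of MRD".

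**Relapse and MRD positivity in the design sections.** In SAP 6.1, and likewise in Protocol 4.1, relapse also includes "development of MRD positivity after having a post-treatment MRD negative status". MRD positivity there means CR with "detection in blood, bone marrow or any other tissues by flow cytometry and/or molecular testing (eg, PCR, next generation sequencing". There is no pretreatment condition.

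**Crossover.** SAP 6.1 admits to Group 2 "Patients in Arm B of Group 1 (SOC) who experience relapse", whether MRD-positive or frank. SAP 6.3.2 states that "SOC patients in Group 1-Arm B who relapse after randomization may cross over to Group 2 to receive MT-401", subject to the subgroup being open and/or Sponsor agreement.

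**Censoring.** If no relapse or death is documented before new anti-cancer therapy, "RFS will be censored on the date of the last evaluable disease assessment demonstrating no relapse prior to analysis cutoff" or before that therapy starts. Protocol Table 9 has a matching row. SAP 7.1 classes re-treatment with MT-401 as follow-up anti-cancer therapy. It does not mention a first course of MT-401 given to an Arm B patient.

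**The concern.** The same MRD result can permit crossover, count as an event for the exploratory time-to-MRD-positivity endpoint (SAP 6.4.1.4), and yet not be an RFS event. If the patient then starts new therapy, follow-up for RFS ends just when the disease has returned. Only Arm B can cross over. An Arm A patient with the same result, if given no new therapy, stays at risk and can be counted later. The censoring would then be informative and would fall mainly on one arm of the primary comparison. The Group 1 interim rules in SAP 7.4.7.3 (futility at a hazard ratio above 1.1, and the conditional-power zones) use the same endpoint.

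The mismatch looks like an omission. Protocol Table 6 adds molecular testing to its row for CR without MRD but not to the molecular-relapse row. SAP Table 2 adds it to neither.

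**Working it through.** **1. The definitions side by side**

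| | RFS event (Protocol Table 6, SAP Table 2) | Relapse/MRD+ that permits crossover (Protocol 4.1, SAP 6.1) |
|---|---|---|
| Assay | RT-qPCR or MFC | flow cytometry or molecular testing, with PCR and sequencing as examples |
| Prior condition | marker studied pretreatment | an MRD-negative status after treatment |

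The literal gap is a patient positive only by sequencing or another molecular test that is not RT-qPCR. If pretreatment means pre-transplant, it also includes a patient whose MRD was not studied then; Unknown is an allowed stratum level. No section says that MRD positivity permitting crossover is always an RFS event.

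**2. The plan's own figure.** Inputs from SAP 7.6: 90 events, hazard ratio 0.55 (medians of 8 and 14.5 months), two-sided alpha 0.05, 1:1 allocation. Schoenfeld power is Φ(|ln HR|·√90/2 − 1.96) = Φ(0.598 × 4.743 − 1.96) = Φ(0.88) = 80.9%. The stated 80% is reproduced.

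**3. Closed form for the literal reading.** Let q be the assumed share of relapses outside the table. If every such SoC relapse is censored and every such Arm A relapse is still counted without delay, the SoC event hazard is multiplied by (1 − q). The apparent hazard ratio is then 0.55/(1 − q).

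| q | Apparent HR | Power at 90 events |
|---|---|---|
| 5% | 0.579 | 74% |
| 10% | 0.611 | 65% |
| 20% | 0.688 | 43% |
| 30% | 0.786 | 21% |

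**4. Simulation of the same case.** 3,000 trials per setting, exponential times, 75 per arm, 50 months' accrual, unstratified log-rank test at 90 counted events. Affected SoC patients are censored at once. Affected Arm A patients are counted at a later relapse that meets the table, after a mean lag of 0, 3 or 6 months.

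| q | SoC relapses censored | Estimated HR | Power |
|---|---|---|---|
| 0% | 0 | 0.54 | 80% |
| 5% | about 3 | 0.55–0.57 | 72–77% |
| 10% | about 5 | 0.57–0.60 | 63–72% |
| 20% | about 11 | 0.62–0.69 | 40–59% |
| 30% | about 18 | 0.67–0.78 | 21–42% |

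With no true effect and a 3-month lag, the chance of a false win for MT-401 falls from 2.5% to 1.3% (q = 10%) and 0.5% (q = 20%). If every such positivity is counted in both arms, power is 79–81% for all q.

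**5. Relaxing the one-sided assumption.** 2,000 trials per setting, median lag 3 months to haematologic relapse.

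| New therapy after a positive result outside the table | Power at q = 10 / 20 / 30% |
|---|---|
| All SoC at once, no Arm A | 70 / 56 / 35% |
| Half of SoC, no Arm A | 74 / 70 / 61% |
| All SoC, half of Arm A | 75 / 69 / 57% |
| Equal use in both arms (half or all) | 78–81% throughout |

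These models simplify. They do not separate deaths from relapses, so q acts as a share of all first RFS events. The step 4 model censors at the relapse itself, not at the preceding relapse-free assessment.

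**The case against.** **The censoring is inferred, not written.** The SAP 6.1 relapse definition is study-wide, and Protocol Table 9 censors only therapy started without relapse. A patient crosses over because relapse has been declared, so counting that patient as an event is an available reading. That stands as a possibility. But the RFS text points to the table, and nothing connects the two definitions, so the result would depend on which reading is programmed.

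**Pretreatment may mean the post-transplant baseline.** Every Group 1 patient needs a central MRD result before randomization. On that reading the condition is always met and only the assay gap remains. A reader might infer that patients with Unknown pre-transplant MRD can never have a molecular RFS event; the documents do not establish this.

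**SoC patients are not simply censored at the moment of relapse.** That stronger reading is tempting, but the SAP's censoring date is the last relapse-free assessment. Crossover also needs an open subgroup and/or Sponsor agreement, renewed consent and confirmed eligibility. A relapse meeting the table before new therapy starts is still an event.

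**Arm A is not immune.** Its patients may be re-dosed (Protocol 6.6), which SAP 7.1 does class as anti-cancer therapy, or may receive other treatment. The larger power losses come from assumed complete asymmetry between arms, as step 5 shows.

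**A bias towards 1 costs power and does not create a false positive.** This is correct for the literal reading. However, the trial is open-label, interim RFS is investigator-determined, and independent review is optional. If sites recorded crossover positivity as relapse in Arm B while the same result in Arm A went uncounted, the bias would favour MT-401.

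**Conclusion.** The inconsistency is in the current text of both documents and leaves the primary event incompletely defined. Applied literally, and if crossover MT-401 or bridging is new anti-cancer therapy, the rules can censor some SoC relapses informatively and move the hazard ratio towards 1. Uneven recording by sites could move it the other way.

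The size cannot be read from the documents, which name no central assay and give no rate of positivity outside the table. If central testing uses only MFC or RT-qPCR, few patients may be affected. The power ranges in step 4 are conditional on an assumed share, immediate and complete SoC crossover, and no new therapy in Arm A. They are not forecasts. With equal use of new therapy in both arms the loss is about nil. The point holds because the definition is unsettled, whatever the eventual number of patients.

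**What to change.** - Use one molecular-relapse definition for RFS in Protocol Table 6 and SAP Table 2, matching Protocol 4.1 and SAP 6.1: MRD positivity by flow or molecular testing after an MRD-negative result. Remove the pretreatment condition or define it as the post-transplant baseline.
- Apply it identically in both arms: any MRD positivity that meets it is an RFS event on its assessment date, whether or not the patient crosses over.
- State that crossover MT-401 and bridging therapy are new anti-cancer therapy for RFS.
- Add molecular testing to the SAP Table 2 row for CR without MRD, to match the protocol.
- Add a sensitivity analysis using the current Table 2 definition.

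The cost is an amendment to the wording of the primary event in both documents and one extra analysis. It should be settled before unblinded interim data are seen. No crossover rule or test changes.

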6.4.1.2 Primary Efficacy Variables

Phase 2 Adjuvant (Group 1):

- RFS: defined as the time between the date of randomization and the date of first relapse per ELN recommendations or death by any cause, whichever occurs first. Relapse includes either hematologic and/or molecular relapse as defined in [Table 2](#) at any disease assessment. In the event that no relapse or death is documented prior to analysis cutoff or the start of new anti-cancer therapy, RFS will be censored on the date of the last evaluable disease assessment demonstrating no relapse prior to analysis cutoff or the start of new therapy. For patients who remain alive and have no baseline disease assessment or have no post-randomization disease assessment, RFS will be censored on the date of randomization. In addition, if relapse or death occurs after extended time without disease assessments, RFS will be censored on the date of the last evaluable disease assessment prior to the missed disease assessments.

For patients with relapse or death, a variable will be created to flag whether the earlier date of relapse or death occurs after extended time without disease assessments. The extended time is defined as below:

- Time from randomization date to Day 0 visit + 12 weeks + assessment window of 2 weeks, if the latest assessment prior to the event (relapse or death, whichever is earlier) \leq randomization date + 0.5*time from randomization date to Day 0 visit. For patients without Day 0 visit, an artificial Day 0 visit will be derived as randomization date + mean time from randomization date to Day 0 visit date in MT-401 arm, for analysis purpose only.
- 24 weeks + assessment window of 2 weeks, if the latest assessment prior to the event (relapse or death, whichever is earlier) \leq Day 0 visit + 6 weeks & $>$ randomization date + 0.5*time from randomization date to Day 0 visit
- 38 weeks + assessment window of 5 weeks, if the latest assessment prior to the event (relapse or death, whichever is earlier) \leq Day 0 visit + 18 weeks & $>$ Day 0 visit + 6 weeks
- 78 weeks + assessment window of 5 weeks, if the latest assessment prior to the event (relapse or death, whichever is earlier) \leq Day 0 visit + 37 weeks & $>$ Day 0 visit + 18 weeks
- 104 weeks + assessment window of 5 weeks, if the latest assessment prior to the event (relapse or death, whichever is earlier) \leq Day 0 visit + 78 weeks & $>$ Day 0 visit + 37 weeks

Phase 2 Active Disease (Group 2):

- CR: For Subgroup C, CR is defined as the proportion of patients who achieve a best response of CR_{MRD-} or CR using the ELN recommendations. For Subgroup D, CR rate is defined as the proportion of treated patients who achieve a best response of CR_{MRD-}. Best overall response (BOR) is defined as the best response designation recorded between the date of first dose and the date of objectively documented relapse per ELN recommendations or the date of subsequent therapy, whichever occurs first. For patients without documented relapse or subsequent therapy, all available response designations will contribute to the BOR assessment.
 - The incidence of converting MRD+ to MRD- was chosen as the primary endpoint for Subgroup D based on the following rational: (1) 2017 ELN recommendations (Döhner et al, 2017) introduced a new response category of CR MRD- recognizing MRD assessment provides a more reliable predictor of outcome than morphological assessment and MRD status has been consistently shown to be an independent prognostic marker for disease outcome (Short et al, 2020; Schuurhuis et al, 2018). (2) Given the nature of single arm design, a binary endpoint was considered a more appropriate primary endpoint than a time to event endpoint such as RFS or OS.
- DOCR: For Subgroup C, DOCR is defined as the time between the date of first documented response of CR_{MRD-} or CR to the date of the first documented relapse per ELN recommendations or death due to any cause, whichever occurs first. For Group 2 Subgroup D, duration of complete response is defined as the time between the date of first documented response of CR_{MRD-} to the date of the first documented relapse per ELN recommendations or death due to any cause, whichever occurs first. For patients who neither relapse nor die prior to analysis cutoff or the start of new anti-cancer therapy, DOCR will be censored on the date of their last evaluable disease assessment on or after the assessment of first documented CR and prior to analysis cutoff or start of new therapy.

6.4.1.3 *Secondary Efficacy Variables*

Safety Lead-in (Cohorts I and II) and Cohorts III-V:

- CR (Active disease patients): defined as above for Group 2
- DOCR (Active disease patients): defined as above for Group 2

Phase 2 Adjuvant (Group 1):

- OS: defined as the time between the date of randomization and the date of death. A patient who has not died will be censored on their last contact date (“last known alive date”).
- Graft-versus-host disease RFS (GRFS): defined as the time from randomization to date of GVHD, relapse, or death, whichever occurs first. A GVHD event is defined as any grade

3-4 acute GVHD or chronic GVHD requiring systemic therapy. A patient who has not experienced any of these events prior to analysis cutoff or the start of new anti-cancer therapy, will be censored on the earlier date of their last GVHD assessment and evaluable disease assessment demonstrating no relapse prior to analysis cutoff or start of new therapy. For patients who remain alive and have no baseline disease assessment or have no recorded post-randomization disease assessment, GRFS will be censored on the date of randomization. In addition, if a GVHD event, relapse, or death occurs after extended time without GVHD assessments, GRFS will be censored on the date of the last evaluable GVHD assessment prior to the missed GVHD assessments or on the date of the last GVHD assessment prior to the missed GVHD assessments.

Phase 2 Active Disease (Group 2):

- ORR: defined as the proportion of treated patients who achieve a best response of CR_{MRD}-, CR, CRi, MLFS, or PR using the ELN recommendations and repeated MRD assessment. This endpoint only applies to Group 2 Subgroup C.
- DOR: defined as the time between the date of first documented response of CR_{MRD}-, CR, CRi, MLFS, or PR to the date of the first documented progression per ELN recommendations or death due to any cause, whichever occurs first. For patients who neither progress nor die prior to analysis cutoff or the start of new anti-cancer therapy, DOR will be censored on the date of their last evaluable disease assessment on or after the assessment of first documented CR_{MRD}-, CR, CRi, or PR and prior to analysis cutoff or start of new therapy. This endpoint only applies to Group 2 Subgroup C.
- PFS: defined as the time between the date of first dose and the date of documented progression or death by any cause, whichever occurs first. For patients who remain alive and whose disease has not progressed prior to analysis cutoff or the start of new anti-cancer therapy, PFS will be censored on the date of last evaluable disease assessment prior to analysis cutoff or start of new therapy. For patients who remain alive and have no baseline disease assessment or have no recorded post-dose disease assessment, PFS will be censored on the date of first dose of study medication. This endpoint only applies to Group 2 Subgroup C.
- OS: defined as above for Group 1 except starting at date of first dose of study medication rather than date of randomization.
- RFS (for patients who achieve CR following bridging therapy and for Group 2 Subgroup D patients): defined as above for Group 1 except starting at date of first dose of study medication rather than date of randomization
- GRFS (for patients who achieve CR following bridging therapy and for Group 2 Subgroup D patients): defined as above for Group 1 except starting at date of first dose of study medication rather than date of randomization

6.4.1.4 *Other Efficacy Variables*

Other efficacy endpoints include: markers of immune function, cell targeting, signaling pathways and disease status, including MRD.

Phase 2 Adjuvant (Group 1):

- Time to MRD positivity: defined as the time between the date of randomization and the date of first occurrence of MRD⁺. In the event that no MRD⁺ is documented prior to analysis cutoff or the start of new anti-cancer therapy, time to MRD positivity will be censored on the date of the last MRD status assessment demonstrating MRD⁻ prior to analysis cutoff or start of new therapy. For patients who remain alive and have no baseline MRD assessment or have no post-randomization MRD assessment, time to MRD positivity will be censored on the date of randomization.

Phase 2 Active Disease (Group 2 CR patients):

- Clearance of MRD: defined as the time between the date of first dose and the date of first occurrence of MRD⁻. This endpoint will be assessed in patients whose best overall response is CR MRD-.

Phase 2 Active Disease (Group 2):

- PRO questionnaire: details regarding the PRO questionnaire and associated instructions will be provided in a separate document.

6.4.2 *Description of Safety Variables*

6.4.2.1 *Dose Limiting Toxicities (DLTs)*

A DLT is defined as one of the following AEs reported during the Safety Lead-in observation period (28 days from the day of the initial MT-401 infusion), if considered to be related to MT-401 and deemed clinically significant by the investigator; and fulfills any of the following criterion using National Cancer Institute Common Terminology Criteria for Adverse Events (NCI CTCAE) (Version 5.0) with the exceptions as noted below:

- 1) Grade 3-4 GVHD
- 2) Grade 3-4 toxicity felt to be related to, or resulting from cytokine release syndrome (CRS)
 - Exception: Grade 3 and 4 expected reactions seen with the use of T cell-based immunotherapy, such as (but not limited to) fever and hypotension not requiring pressor support, will not be considered DLTs
- 3) Grade 3-4 infusion reactions that are persistent beyond 72 hours despite optimal medical management

- 4) Any other Grade 3-4 toxicity that is **not** pre-existing and/or **not** due to the underlying malignancy or infection or treatment of disease lasting for extended period of time despite optimal supportive care (for example, nausea, vomiting, and diarrhea lasting > 3 days; fatigue lasting > 7 days)
 - Exception: Laboratory abnormality deemed not to be clinically significant
- 5) Grade 5 toxicity (that is, death)

6.4.2.2 *Adverse Events*

An AE is any untoward medical occurrence in a patient or clinical study patient, temporally associated with the use of MT-401, whether or not considered related to MT-401. An AE can therefore be any unfavorable and unintended sign (including an abnormal laboratory finding), symptom, or disease (new or exacerbated) temporally associated with the use of MT-401.

6.4.2.3 *Laboratory Parameters*

Clinical laboratory tests will be collected at the specified time points indicated in the schedule of assessments in Section 1.2.1 of the clinical study protocol. Laboratory tests to be collected (on days of MT-401 administration, labs should be performed prior to MT-401 administration) include hematology, serum chemistry, and coagulation tests.

6.4.2.4 *Vital Signs*

Vital signs will be performed at the specified time points indicated in the schedule of assessments in Section 1.2.1 of the clinical study protocol. Temperature, pulse rate, and blood pressure will be assessed, and if clinically indicated, respiratory rate will also be assessed.

6.4.2.5 *Physical Examination*

Physical examinations will be performed at the specified time points indicated in the schedule of assessments in Section 1.2.1 of the clinical study protocol. A complete physical examination will be performed as per institutional guidelines at baseline and will include, at a minimum, assessments of the Cardiovascular, Respiratory, Gastrointestinal and Neurological systems, and height (at Screening) and weight will also be measured and recorded. A brief physical examination will include, at a minimum, assessments of the Cardiovascular, Respiratory, and Gastrointestinal systems.

6.4.2.6 *GVHD Assessments*

A potential toxicity for patients receiving allogeneic T cells is GVHD. The risk that adoptively transferred leukemia-targeted T cells will cause GVHD is very low. GVHD will be assessed at the specified time points indicated in the schedule of assessments in Section 1.2.1 of the clinical study protocol and as per acute and chronic GVHD guidelines ([Harris, et al 2016](#); [Jagasia et al, 2015](#)).

